## 2 AIMS

This study aims to evaluate the implementation and effectiveness outcomes of TranS-C in the CMHCs of counties across California in the United States. As explained above, the present protocol describes Phase 2, the Train-the-Trainer Phase, of a three-part hybrid type 2 effectiveness-implementation study. The Train-the-Trainer Phase builds upon the infrastructure of the Implementation Phase (42). Specifically, during the Implementation Phase, sites are cluster-randomized by county to Adapted TranS-C or Standard TranS-C with 1:1 allocation. External expert trainers train an initial cohort of providers (i.e., Generation 1 providers) in TranS-C via facilitation. Then, within each county, patients are randomized to receive

immediate TranS-C or UC-DT from Generation 1 providers.

In the Train-the-Trainer Phase, expert trainers offer additional training for Generation 1 providers to become “local trainers” in TranS-C. Then, these local trainers train the next cohort of providers (i.e., Generation 2 providers) within their organization in TranS-C (see Figure 1). Then, within each county, patients are randomized to receive immediate TranS-C or UC-DT from Generation 2 providers. Patients treated by Generation 2 providers are referred to as “Generation 2 patients.” Sites retain their original randomization assignment to Adapted or Standard TranS-C. See below for more details on the TTT procedures.

Aims and hypotheses for the Train-the-Trainer Phase mirror the Implementation Phase (42). Parallel analyses to the Implementation Phase will allow us to test the extent to which implementation and effectiveness outcomes are maintained with TTT.

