The first aim is to assess the effectiveness of TranS-C, compared to UC-DT, in patients who are treated by Generation 2 providers. We hypothesize that, compared to UC-DT, TranS-C (combined Adapted and Standard) will be associated with larger reductions in the primary patient outcome of sleep disturbance and the secondary patient outcomes of sleep-related impairment, functional impairment, and psychiatric symptoms. We also hypothesize that TranS-C’s benefits for functional impairment and psychiatric symptoms will be mediated by improvements in sleep and circadian problems. The second aim is to evaluate whether TranS-C treatment condition (Adapted vs. Standard TranS-C) is associated with fit to the CMHC context, operationalized as provider ratings of acceptability, appropriateness, and feasibility, for Generation 2 providers. We hypothesize that Adapted TranS-C will be superior to Standard TranS-C with respect to the primary provider outcome of acceptability and the secondary provider outcomes of appropriateness and feasibility. The third aim is to evaluate whether perceived fit among Generation 2 providers mediates the relation between TranS-C treatment condition and Generation 2 patient outcomes. We hypothesize that relative to Standard TranS-C, Adapted TranS-C will be associated with greater reductions in the primary and secondary patient outcomes indirectly through higher provider ratings of acceptability, appropriateness, and feasibility. Exploratory analyses will: (1) compare whether the effectiveness of TranS-C for primary and secondary patient outcomes is moderated by generation, (2) compare Adapted and Standard TranS-C on Generation 2 patient perceptions of credibility and perceived improvement and select PhenX Toolkit outcomes that are both strongly related to SMI and sleep and circadian problems (e.g., substance use, suicidality) (43–46) and of high priority to our community partners; and (3) determine whether treatment effects for Generation 2 patients are moderated by risk factors including age, sex, and sleep and circadian and psychiatric symptoms at baseline. In particular, emerging evidence suggests that patients who are older and have more severe sleep and circadian and psychiatric symptoms at baseline demonstrate poorer response to sleep and circadian treatment, whereas outcomes by sex have been mixed for patients with SMI (47,48).

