#### **4.7 Exploratory Aim 1: Generation 1 Compared to Generation 2 on Patient Outcomes**

To compare Generation 1 and Generation 2 on primary and secondary patient outcomes of TranS-C, data from the Implementation Phase (see Sarfan et al., 2023) and the TTT Phase and both TranS-C conditions (Adapted and Standard) will be combined. MLM will be used to evaluate interactions between generation (Generation 1 or Generation 2) and time. The level 1 equation will include dummy-coded time indicators as the predictors (0 = pre-treatment, 1 = post-treatment). The level 2 equation will include dummy-coded generation (0 = Generation 1, 1 = Generation 2) and treatment by time interaction terms as predictors, adjusting for county. A significant interaction indicates a moderating effect of generation and will be probed with planned contrasts (e.g., effects of generation on change from pre-treatment to post-treatment) and graphs.

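### Exploratory Aim 1 reads a generation-by-time interaction as moderation of TranS-C's effectiveness, but section 4.7 has no generation × treatment × time term

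*Combined protocol and SAP*

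**What the plan says.** - **Question.** Section 2 (Aims) says the first exploratory analysis will "compare whether the effectiveness of TranS-C for primary and secondary patient outcomes is moderated by generation". The Abstract poses the same question. In the same section, effectiveness under Aim 1 is relative to a control: "The first aim is to assess the effectiveness of TranS-C, compared to UC-DT, in patients who are treated by Generation 2 providers".
- **Data.** Section 4.7 brings together the Implementation Phase and the Train-the-Trainer Phase, and "both TranS-C conditions (Adapted and Standard) will be combined". It does not mention UC-DT.
- **Tested term.** "MLM will be used to evaluate interactions between generation (Generation 1 or Generation 2) and time".
- **Level 2 predictors.** "dummy-coded generation (0 = Generation 1, 1 = Generation 2) and treatment by time interaction terms as predictors, adjusting for county". Treatment is not coded or defined in section 4.7.
- **Interpretation.** "A significant interaction indicates a moderating effect of generation".
- **Controls available.** Section 2 says Implementation Phase patients are randomised to "immediate TranS-C or UC-DT from Generation 1 providers", and describes the same patient-level randomisation for Generation 2.
- **Other moderators.** Section 4.9 tests age, sex and baseline symptoms with a three-way interaction of moderator, time and TranS-C versus UC-DT.

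**The concern.** Moderation of effectiveness by generation means that the TranS-C versus UC-DT difference in change is not the same in the two generations. That is a three-way contrast. The term that section 4.7 tests and interprets is a two-way contrast, which also contains any difference between generations in how patients would have changed without TranS-C.

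Generation is not randomised. Section 3.1 describes a rolling move of sites to Train-the-Trainer between December 2020 and December 2022, a period whose COVID-19 disruption the protocol itself stresses. Section 3.3.1 adds that one county left and another was recruited. Section 4.7 adjusts for county, which section 4.1 says enters as a factor. A county main effect shifts the level of the outcome, not its change over time, and no county-by-time or calendar-time term is stated. The sensitivity analyses in section 4.6 cover Aims 1–3 only.

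Section 1 presents the maintenance of outcomes from Generation 1 to Generation 2 as the fundamental question for train-the-trainer studies, and section 4.7 is the plan's direct comparison of the generations. Background drift could produce an apparent generation effect where there is none, or hide a real loss of benefit.

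**Working it through.** The documents give no sample size, power or detectable effect for Exploratory Aim 1, so there is no stated figure to reproduce.

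**1. What each term estimates.** For generation g, let s_g be the mean change under usual care and τ_g the extra change due to TranS-C.

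- UC-DT omitted: generation × time = (s₂ + τ₂) − (s₁ + τ₁) = (τ₂ − τ₁) + (s₂ − s₁).
- UC-DT included with treatment × time but no three-way term, equal arms: the generation coefficient averages the control difference (s₂ − s₁) and the treated difference (s₂ − s₁) + (τ₂ − τ₁). It equals (s₂ − s₁) + ½(τ₂ − τ₁).
- Three-way term: generation × treatment × time = τ₂ − τ₁.

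On the first two readings drift enters one-for-one. On the second, only half of a true difference in effect is recovered. Reading treatment as Adapted versus Standard, or as a slip for generation, falls under the first.

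**2. Inputs.**

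- Generation 2: 130 patients (section 3.8). With 1:1 allocation assumed, 65 are immediate.
- Generation 1: not given separately. Section 3.8 states only a goal of 576 for both phases combined. Assumed range: 100–220 immediate patients.
- Two-sided 5% level, as for the main aims (assumed to apply here).
- Drift s₂ − s₁ of 0.1–0.3 SD of change (assumed; no document reports one).
- Clustering, attrition and county adjustment ignored.

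**3. Rejection rate with no true moderation, UC-DT omitted.** In SD-of-change units, SE = √(1/n₁ + 1/n₂), and the rejection rate is P(|Z + drift/SE| > 1.96).

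- n₁ = 100: SE = √(1/100 + 1/65) = 0.159.
- n₁ = 220: SE = √(1/220 + 1/65) = 0.141.

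| Drift (SD of change) | n₁ = 100 | n₁ = 220 |
|---|---|---|
| 0 | 5% | 5% |
| 0.1 | 10% | 11% |
| 0.2 | 24% | 29% |
| 0.3 | 47% | 57% |

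**4. Simulation check.** 3,000 replicates on change scores, 130 Generation 2 patients, 446 Generation 1 patients (576 − 130, an assumption), equal arms. Negative values mean improvement.

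| Scenario | UC-DT omitted | UC-DT in, no three-way term | Three-way term |
|---|---|---|---|
| No moderation, no drift | 0.00; 5.5% | 0.00; 5.3% | 0.00; 4.7% |
| No moderation, drift −0.3 | −0.30; 58% | −0.30; 86% | −0.01; 4.9% |
| Benefit falls by 0.3, drift −0.3 | 0.00; 4% | −0.15; 33% | 0.30; 33% |

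Cells give the mean estimate and the rejection rate. In the last row the TranS-C-only test hides a real loss of benefit. With UC-DT in and no three-way term, the estimate has the wrong sign. The three-way estimate is right on average but detects the loss only a third of the time.

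**5. Precision of the three-way term.** It adds two control-arm variances. With equal arms the SE is √2 ≈ 1.41 times larger: 0.225 (n₁ = 100) or 0.200 (n₁ = 220). At 80% power the detectable difference (2.80 × SE) rises from 0.45 to 0.63 SD, or from 0.40 to 0.56 SD.

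**The case against.** The strongest reply is that section 4.7 sets out to compare the generations on patient outcomes of TranS-C, and section 1 asks whether key outcomes are maintained. Change under TranS-C in each generation speaks to that directly, without a control. This stands for a descriptive comparison. It does not cover the Abstract and section 2, which speak of effectiveness, or section 4.7's own reading of the interaction as moderation.

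A reader might go further than the documents allow in three ways.

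- **That the model is stated to use TranS-C patients only.** It is not. UC-DT is never excluded, treatment is undefined, and section 2 uses similar wording on combining Adapted and Standard for a comparison with UC-DT. Omission is the natural reading, but the point holds on either.
- **That the plan has no other evidence on maintenance and can support no conclusion.** Section 2 says parallel analyses to the Implementation Phase will address maintenance, and Aim 1 gives a randomised, concurrently controlled estimate in Generation 2. That is not a direct test of a difference between generations, but it is controlled evidence.
- **That calendar change will be mistaken for a generation effect.** This happens only if background change differs between periods. The rolling transition may also give some calendar overlap between counties.

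The three-way term has limits of its own. It costs precision, and a non-significant result would say little about maintenance.

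**Conclusion.** The concern holds in a limited form. The interaction tested in section 4.7 does not match the moderation question in section 2, and no reading of the section supplies the missing term. Both phases have randomised UC-DT arms, and section 4.9 already uses the matching structure for other moderators.

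The algebra needs no assumed numbers. The rejection rates (about 10–11%, 24–29% and 47–57% at drifts of 0.1, 0.2 and 0.3 SD) rest on assumed drifts, an assumed Generation 1 size, 1:1 allocation and no clustering. They illustrate sensitivity and are not an expected error rate.

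Nor should the three-way term be taken to make the generation comparison causal. It removes additive background change, but a difference in period, provider type or patient mix that alters the TranS-C effect would still appear as a generation effect. The aim is exploratory and no primary analysis depends on it, so this should be corrected but does not threaten the main conclusions.

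**What to change.** In section 4.7:

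1. State that UC-DT patients from both phases are included, and code treatment 0 = UC-DT, 1 = Adapted or Standard TranS-C.
2. Fit generation, treatment, time, all two-way terms and generation × treatment × time. Name the three-way term as the moderation test, matching section 4.9, and replace the undefined treatment-by-time wording.
3. Report the three-way estimate with its confidence interval, and do not read non-significance as evidence that effectiveness is maintained.
4. Keep generation × time within TranS-C as a labelled descriptive comparison of outcomes, not as evidence of moderation.
5. State that generation is not randomised, so effect modification by period, provider or patient mix remains possible.

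The cost is a revised paragraph and one re-specified model, using arms that both phases randomise by design. The statistical price is the lower precision shown in step 5 of the working.

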#### **4.8 Exploratory Aim 2: TranS-C Treatment Condition on PhenX Toolkit and Perceived Credibility and Improvement**

MLM will be used to test TranS-C treatment condition (Adapted vs. Standard TranS-C) predicting change in PhenX Toolkit outcomes of substance use and suicidality from pre-treatment to post-treatment and pre-treatment to 6FU in Generation 2. The approach to MLM will mirror Aim 2, except the focus will be the Generation 2 patient data, outcomes will be substance use and suicidality from the PhenX Toolkit, and models will evaluate change from pre-treatment to 6FU. Linear regression will be used to test treatment

condition (Adapted vs. Standard TranS-C) predicting patient perceptions of TranS-C's credibility and perceived improvement at post-treatment.

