### **3.4.1 Standard TranS-C**

Standard TranS-C is delivered in 8x50 minute weekly sessions and comprised of 4 *cross-cutting modules* featured in every session, 4 *core modules*, and 7 *optional modules* that are used based on clinical presentation, treatment goals, and provider case conceptualization (27). Training for providers in the Standard TranS-C condition consists of a 1-day workshop (i.e., 6-8 hours) or two, 3-hour training blocks.

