### **3.4.2 Adapted TranS-C**

Adapted TranS-C is delivered in 4x20 minute weekly sessions and comprised of the same four *cross-cutting* and *core modules* as in Standard TranS-C. Modifications include (1) the *cross-cutting modules* are standardized across sessions and scripted (to reduce preparation time) and (2) the core modules are split up into five (rather than four) modules. Additionally, there is one *optional module* which can be integrated with the core modules, based on clinical presentation, treatment goals, and provider case conceptualization. Training for the Adapted TranS-C condition consists of four, 1-hour workshops or two, 2-hour workshops, based on CMHC preferences.

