### **3.4.3 UC-DT**

In UC-DT, patients begin with usual care for four weeks if their CMHC is randomized to Adapted TranS-C or eight weeks of usual care if their CMHC has been randomized to Standard TranS-C. After the delay, they receive Adapted or Standard TranS-C, also based on the condition to which their CMHC has been randomized (see Figure 2). The decision to compare TranS-C to UC-DT was made in close collaboration with the early CMHC partners. This design aims to strike a balance between (a) including a comparison group to demonstrate the effectiveness of TranS-C in community settings; (b) ensuring that all participants receive what we hypothesize to be an active treatment (TranS-C); and (c) maximizing efficiency in terms of study duration, budget, and participants' time investment. Notably, usual care has been the comparison group in several influential studies (64–66).

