### 3.5.2.3 Exploratory Outcomes

*PhenX Toolkit: Substance Use and Suicidality.* Scales from the PhenX Toolkit (73) are used to assess various patient outcomes, including suicidal ideation and behaviors, alcohol, tobacco, and other psychoactive substances (e.g., cannabis, hallucinogens, sedatives, etc.). PhenX measures have been compiled by working groups and domain experts via a consensus process to facilitate consistency across studies (73). To assess suicidal ideation and behaviors, the PhenX ‘Classification of Suicidal Ideation and Suicidal Behavior - Adult - Current’ protocol is used. This protocol includes two subscales from the screening version of the Columbia-Suicide Severity Rating Scale: Severity of Suicidal Ideation and Suicidal Behavior, assessing suicidality during two time periods—namely ideation in the past month and suicidal behavior in the past three months. To ease patient burden, this measure was adapted slightly, such that if patients deny suicidal ideation, they are not required to answer questions about suicidal behavior. To assess alcohol, the PhenX ‘Alcohol - 30-Day Quantity and Frequency’ protocol is used. This protocol measures both quantity and frequency of alcohol consumption. To assess tobacco, the PhenX ‘Tobacco - 30-Day Quantity and Frequency - Adult’ protocol is used. This measure has three sets of question protocols: (1) a protocol for ‘Every-Day Smokers,’ (2) a protocol for ‘Some-Day Smokers,’ and (3) a protocol for ‘Former Smokers.’ If patients report that they have never smoked tobacco, this measure is skipped. To assess use of substances and other drugs, the PhenX ‘Substances - 30-Day Frequency’ protocol is used. This measure assesses use of substances such as sedatives, painkillers, stimulants and hallucinogens. In addition, caffeine is assessed using questions adapted from the ‘Supplemental Beverage Questionnaire.’ Questions used in the present study assess frequency and quantity of caffeinated or decaffeinated drinks consumed over the past 30 days.

*Credibility and Perceived Improvement.* Perceptions of TranS-C credibility and perceived symptom improvement are assessed by four questions adapted from the Credibility/Expectancy Questionnaire (CEQ) (74). These questions assess (1) how logical TranS-C seemed, (2) how successful it was in

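### Exploratory Aim 2's pre-to-post contrast of Adapted and Standard on suicidal behaviour uses a three-month recall over 4- and 8-week courses, so change is diluted more in Adapted

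*Combined protocol and SAP*

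**What the plan says.** Section 4.8 (Exploratory Aim 2) uses multilevel models with TranS-C version "predicting change in PhenX Toolkit outcomes of substance use and suicidality from pre-treatment to post-treatment" and from pre-treatment to 6FU. It adds that the approach mirrors Aim 2, except among other things that "models will evaluate change from pre-treatment to 6FU". Section 4.1 also names both intervals for Adapted-versus-Standard comparisons.

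Section 3.5.2.3 gives the recall periods for suicidality: "namely ideation in the past month and suicidal behavior in the past three months". Patients who deny ideation need not answer the behaviour questions. The alcohol and tobacco protocols look back 30 days, as does the "Substances - 30-Day Frequency" protocol.

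The two versions differ in length. Section 3.4.1: "Standard TranS-C is delivered in 8x50 minute weekly sessions". Section 3.4.2: "Adapted TranS-C is delivered in 4x20 minute weekly sessions". The usual-care delay follows the same split (section 3.4.3): "patients begin with usual care for four weeks if their CMHC is randomized to Adapted TranS-C or eight weeks of usual care".

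Table 2 shows the PhenX measures collected at pre-treatment, post-treatment and 6FU. Nothing in the document relates the recall periods to course length, or ranks 6FU above post-treatment for these outcomes. The assessment-timing sensitivity analysis in section 4.6 covers Aims 1-3 only.

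**The concern.** A change score is meant to compare a period before treatment with a period under or after it. When the recall period is longer than the course, part of the post-treatment answer describes time before treatment began. A longer course leaves less of that, so the same true effect produces different measured change in the two versions. The version itself determines the overlap, so neither randomisation, nor adjustment for county, nor a larger sample removes the difference.

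Section 2 describes the PhenX outcomes as a high priority for the community partners. A post-treatment estimate suggesting that the shorter version does less for suicidal behaviour could come partly from the question's look-back period and be read as a property of the version.

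**Working it through.** The plan gives no sample size, power or effect figure for Exploratory Aim 2, so there is no stated figure to reproduce. The check is recall-window arithmetic.

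**Inputs**
- Recall W: three months, taken as 91 days, for suicidal behaviour; 30 days for substances, alcohol and tobacco; one month, taken as 30 days, for ideation (section 3.5.2.3).
- Course length T: 28 days for Adapted and 56 for Standard (sections 3.4.1 and 3.4.2, consistent with the delays in section 3.4.3).
- Lag L from end of treatment to the post-treatment assessment: not given. Assumed 0 to 28 days, equal in both versions.

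**Formula.** Recall days before treatment = max(0, W − (T + L)). Divide by W for the share.

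**Suicidal behaviour, W = 91**

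| Lag | Adapted | Standard |
|---|---|---|
| 0 days | 91 − 28 = 63 (69%) | 91 − 56 = 35 (38%) |
| 14 days | 91 − 42 = 49 (54%) | 91 − 70 = 21 (23%) |
| 28 days | 91 − 56 = 35 (38%) | 91 − 84 = 7 (8%) |

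If the sessions span 21 and 49 days from first to last, the lag-0 shares are 70/91 = 77% and 42/91 = 46%.

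**Effect on measured change.** Suppose both versions have the same full effect from day 0. At lag 0 the post-treatment item captures 28/91 = 31% of it in Adapted and 56/91 = 62% in Standard, a two-fold difference. If the effect instead grows linearly to the end of each course, these shares halve to 15% and 31%; the ratio is the same.

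**Skip rule.** Let q be the share of patients with earlier behaviour who still endorse past-month ideation at post-treatment, assumed equal in both versions. Recorded carry-over at lag 0 is then 0.69q against 0.38q. At q = 0.5 that is 35% against 19%. The amount falls, but the ratio stays at 63/35 = 1.8 for any q above zero.

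**30-day and past-month items, W = 30.** At lag 0: 30 − 28 = 2 days (7%) in Adapted and 0 in Standard. With a lag of 2 days or more, both are 0. If Adapted's sessions span only 21 days, the overlap at lag 0 is 9 of 30 days, gone with a 9-day lag. Under linear growth of effect, the captured share at lag 0 is 14/30 = 47% in Adapted and 41/56 = 73% in Standard; with a 14-day lag it is 85% and 92%.

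**At 6FU.** The assessment falls about 182 days after treatment ends. max(0, 91 − (28 + 182)) = 0 and max(0, 91 − (56 + 182)) = 0. The 30-day windows also give 0.

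**The case against.** The strongest reply is that this is one item, at one of two planned intervals, in an exploratory analysis, and that the unaffected comparison to 6FU is already in the plan. That stands: no primary or secondary conclusion changes. It does not remove the post-treatment contrast, because the first sentence of section 4.8 and section 4.1 both name that interval.

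The skip rule also counts: older behaviour is recorded only from patients who still report recent ideation. As shown above, it shrinks the carry-over without equalising it. How the suicidality outcome is scored is not stated, so the weight of the behaviour item is unknown.

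Three stronger readings are tempting, and the documents do not support them.

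- A reader might extend the point with equal force to substance use and ideation. Direct overlap there is about 2 days at nominal timing and disappears with a 2-day lag. The rest depends on an assumed gradual onset, and is partly the ordinary consequence of comparing courses of different length.
- A reader might infer that the bias always runs against Adapted. It does so only if treatment is beneficial. With no effect there is nothing to dilute, and with worsening the dilution flatters Adapted.
- A reader might expect a false significant result. Assume 10% of patients report behaviour per three months and both versions stop it on day 1. The item would still read 1 − 0.90^(9/13) = 7.0% in Adapted and 1 − 0.90^(5/13) = 4.0% in Standard. These figures rest on an assumed base rate and ignore the skip rule. Even so, with an assumed 65 patients per version (half of the 130 in section 3.8), the chance of p < 0.05 on the post-treatment difference is about 4% (Fisher) to 12% (normal approximation), ignoring clustering and missing data. The problem is a built-in tilt in the estimate more than a likely false headline.

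**Conclusion.** The concern holds for three-month suicidal behaviour at post-treatment. At nominal timing, 69% of the recall window precedes treatment in Adapted against 38% in Standard. The gap is about 31 percentage points at each lag from 0 to 28 days, since 28/91 = 31%. Equally beneficial versions would therefore tend to look different, in favour of Standard.

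This rests on courses of about 28 and 56 days, equal lags in the two versions, and some patients still endorsing ideation at post-treatment. Actual lags are not documented, and longer ones reduce the overlap in both versions. For the 30-day items and past-month ideation, a caveat is enough. The planned comparison at 6FU is free of the problem. The point is a modest, cheap improvement to an exploratory analysis.

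**What to change.** Amend section 4.8 as follows.

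1. For three-month suicidal behaviour, make pre-treatment-to-6FU change the main time point for Adapted versus Standard, since both versions' recall windows then lie wholly after treatment.
2. Report post-treatment suicidal behaviour by version descriptively, with the share of the recall window that precedes treatment, calculated from actual dates.
3. Keep the post-treatment contrast for the 30-day substance items and past-month ideation, with a sentence on recall and course length.

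No new data or visits are needed. The cost is one early exploratory test and reliance on 6FU, where more data may be missing. A difference of about four weeks in time since baseline remains at 6FU, but it does not bring pre-treatment time into either window.
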